## 6.2 Hypothesis and/or Estimation

No hypothesis or estimation is planned on treatment efficacy endpoint for phase 1B section.

## 6.3 Missing Data Handling

In general, missing data will not be imputed; however, missing or partially missing start/end dates for events, such as AEs, concomitant medication use, and initial diagnosis date, will be imputed according to the rules outlined in [Table 1](#). If an event is ongoing, the end date will not be imputed.

**Table 1 Missing Imputation Rules**

Missing variables	Missing Dates	Imputation method
Event start date	Only day is missing	If the month and year of the event start date are the same as those for Study Day 1, the imputed start date will be the same as that for Study Day 1. Otherwise, the imputed start date will be the first day of the known month.
	Both month and day are missing, but year is available	If the year of the event start date is the same as that for Study Day 1, the imputed event start date will be the same as that for Study Day 1. Otherwise, the imputed start date will be Jan 1st.
	Year, month, and day are missing, or only year is missing	No imputation
Event end date	Only day is missing	Impute the last day of the known month. If an event stop day is missing and the event stop month and year are the same as the death month and year, the imputed event stop date will be the date of death.
	Both month and day are missing, but year is available	Impute with min (the date of end of study, December 31 of the known year).
	Year is missing	No imputation
Initial diagnosis date	Only day is missing	Impute the first day of that month
	Both month and day are missing	Impute Jan 1st
	Year is missing	No imputation

#### 6.4 Visit Window

#### 6.5 Nominal visits will be used in the analysis, unless specified otherwise. Data Handling and Electronic Transfer of Data

Analysis Data Model (ADaM) data sets will be prepared for statistical analysis. ADaM data are derived from the Study Data Tabulation Model (SDTM) data. SDTM data are derived from raw data. Raw data consist of data from the electronic case report form (eCRF) and other external data (central/vendor laboratory generated data; imaging and laboratory data). Atara Clinical Data Management is responsible for the collection and receipt of eCRF and central vendor data. The Atara data management standard operating procedure (SOP) will be followed.

## 6.6 Validation of Statistical Analysis

The statistical analysis validation will follow the Atara's validation SOP.

# 7 STUDY SUBJECTS

## 7.1 Study Disposition

**7.2 Subject disposition data will be summarized by sub cohort and overall (ie, all Phase 1B subjects combined); the summary table will include: the number of subjects screened, the number of subjects who failed screening, the number of subjects enrolled, the number of subjects enrolled but not treated, and the number of subjects treated. Treatment status (completed or discontinued) with reasons for treatment discontinuation and end of study status (completed vs. did not complete) with reasons for not completing the study will also be summarized by cohort and overall.**

### Important Protocol Deviations

Important protocol deviations (IPDs) categories are defined by the study team before the first subject's visit and updated during the IPD reviews throughout the study. The categories will be finalized prior to database lock. IPD categories, deviation codes, and descriptions will be used during the course of the study. Subjects with IPDs will be listed with IPD categories, deviation codes, and descriptions.

## 7.3 Demographic and Baseline Characteristics

The following demographic and baseline characteristics will be summarized for the Full Analysis Set by sub-cohort and overall.

- Age at baseline: descriptive statistics and n (%) for Age categories such as < 16, ≥ 16 years and Age <18, ≥ 18 years
- Gender
- Ethnicity
- Race
- Eastern Cooperative Oncology Group (ECOG) performance status descriptive statistics and n (%)
- Time from initial diagnosis to first dose of tabelecleucel (months)
- NPC history factors will be also summarized in this table by n (%) on Lines of systemic treatment, overall disease stage; Distant metastasis; Tumor burden at baseline; Lesion location at baseline.

## 7.4 Prior therapy

Prior therapy will be summarized on Type of therapy, Chemotherapy category, Best Response to Prior therapies.

## 7.5 Extent of Exposure

Summary statistics will be provided for the exposure of pembrolizumab and tabelecleucel, including the total dose of pembrolizumab and the weight-adjusted dose of tabelecleucel, total number of doses administered, number of lots subjects received, number of cycles and duration of treatment, number of restriction switch will be summarized for tabelecleucel.

# 8 EFFICACY ANALYSES

The Full Analysis Set will be the primary analysis set for efficacy analyses.

Efficacy analyses will be conducted separately for subjects who are checkpoint inhibitor naïve or PD-1/PD-L1 failures. The disease assessments will be performed by the investigators.

The exact binomial 2-sided 95% CI will be provided for binary endpoints, ORR.

If any anti-NPC therapy other than specified in the protocol, is initiated, disease assessment data after the initiation date will be censored for the purpose of the efficacy analysis.

Subjects may have post-cycle 1 response of indeterminate response (IR). In the event that a subject with an IR assessment has discontinued the study and has not proceeded to a subsequent assessment (eg, subject is lost to follow up or dies), then the IR response will be considered as progressive disease. If a subject is still on study and has an IR assessment without a subsequent assessment, then the IR response will be considered as not evaluable (NE).

### 8.1 Analysis of the Primary Endpoint

#### 8.1.1 Primary Analysis

The incidence of DLTs (defined in section 5.2.3 of the protocol) will be evaluated for phase 1B part of the study from the subjects in Cohort 1 (by dose level if applicable).

The primary endpoint is ORR (overall response rate), responder is defined as the proportion of subjects who achieved Best Overall Response (BOR) of CR or PR after administration of up to the first 2 tabelecleucel cell products, clinical benefit is defined as the proportion of subjects who achieved Best Overall Response (BOR) of CR or PR or SD after administration of up to the first 2 tabelecleucel cell products. If any new anti-NPC treatment, other than specified in the protocol,

is initiated, response data after the initiation date will not be considered for the definition of response. Disease assessment during the follow-up stage will not be considered for ORR or CBR definition.

The ORR and CBR (clinical benefit response) and their corresponding 95% CI will be reported.

## **9 PHARMACOKINETIC/PHARMACODYNAMIC ANALYSIS**

No pharmacokinetic/pharmacodynamic analysis is planned.

## **10 BIOMARKERS**

No biomarker analysis is planned.

## **11 SAFETY ANALYSES**

### **11.1 Summary of Adverse Events**

MedDRA version 24.0 or later will be used to code AEs to a system organ class (SOC) and a PT within the SOC. The National Cancer Institute Common Terminology Criteria for Adverse Events (CTCAE) version 5.0 will be used to grade severity of AEs. For certain AEs for which CTCAE does not apply, non-CTCAE grades will be applied. The severity grade of non-CTCAE graded AEs are mapped using the following rules and then summarized together with CTCAE graded AEs: mild (grade 1), moderate (grade 2), severe (grade 3), life-threatening (grade 4), or death (grade 5). In addition, for graft-versus-host disease (GvHD), the Center for International Blood and Marrow Transplant Research (CIBMTR) consensus grading system will be used. CIBMTR grading includes an overall grade and separate grades based on rash status, bilirubin level, diarrhea status, and nausea status.

TEAEs are defined as follows:

- Any AE occurring after initiation of the first dose of study treatment through 30 days after the last administration of study treatment or
- Any pre-existing AE (ie, started prior to the first dose of study treatment) that worsened after the first dose through 30 days after the last administration of study treatment or
- Any related AE on or after first dose.

AEs occurring on the same day of the first dose of study treatment will be counted as TEAEs. AEs with complete or partial missing start/end dates will be all considered as treatment-emergent unless

- The partial start date is clearly after the 30 days of the last dose of study treatment. For example, last dose date + 30 days is in November and the AE start date is in the next January with the day missing.

or

- The partial end date is clearly before the first dose date of study treatment. For example, the first dose date is in March while the AE end date is in February with the day missing.

Imputation rules for partial missing dates may be applied to TEAE start/end dates, as described in Section 7.3.

All the AEs collected in this study (whether or not treatment-emergent) will be listed; TEAEs will be summarized as follows:

- Overall Summary of AE including
  - Any TEAEs
  - TEAEs with worst grade  $\geq 3$
  - Fatal TEAEs
  - Serious TEAEs
  - TEAEs leading to any study treatment discontinuation
  - TEAEs leading to any study treatment interruption
  - The above summaries will be repeated for TEAEs that are related or possibly related to study treatment pembrolizumab or tabelecleucel respectively.
- By SOC and PT, sorted by alphabetic order of SOC, then by descending order of PT total frequency
  - Subject incidence of all TEAEs
  - Subject incidence of serious TEAEs
- By PT, sorted by descending order of PT frequency and then by alphabetic order of PT.
  - Subject incidence of TEAEs
  - Subject incidence of serious TEAEs
  - Subject incidence of TEAEs leading to death
  - Subject incidence of TEAEs leading to pembrolizumab or tabelecleucel discontinuation
  - Subject incidence of treatment related TEAEs
  - Subject incidence of treatment related serious TEAEs

- Subject incidence of treatment related TEAEs leading to pembrolizumab or tabelecleucel discontinuation
- By preferred term and worst severity grade
  - Subject incidence of TEAEs
  - Subject incidence of serious TEAEs
  - Subject incidence of treatment related TEAEs
  - Subject incidence of treatment related serious TEAEs
- A summary table of identified and potential risks including TEAEs of special interest (TEAESIs) by PT sorted by risk category and PT in descending order of frequency within a risk category. The Risk categories for tabelecleucel include:
  - infusion-related reactions
  - transmission of infectious disease(s)
  - cytokine release syndrome
  - GvHD event
  - And additional risk of tumor flare.
- A summary table of TEAEs of special interest (TEAESIs) by PT sorted by PT in descending order of frequency for Pembrolizumab include:
  - Overdose- >1000 mg or >/= 5 times the indicated dose
  - Elevated liver values per Pembro label
- A summary table of TEAEs of dose limiting toxicity by PT in descending order of frequency.

The primary cause of all deaths will be summarized.

A listing of all deaths, serious TEAE, and TEAE leading to treatment or study discontinuation, or leading to death will be provided.

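### SAP 11.1's missing-date default can flag AEs as treatment-emergent, or drop them, against the TEAE definition just above it

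*SAP*

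**What the plan says.** SAP Section 11.1 gives a three-limb TEAE definition:

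- Window: "Any AE occurring after initiation of the first dose of study treatment through 30 days after the last administration of study treatment".
- Pre-existing: "Any pre-existing AE (ie, started prior to the first dose of study treatment) that worsened after the first dose", with the same 30-day upper limit.
- Related: "Any related AE on or after first dose", with no upper time limit.

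A default for incomplete dates follows: "AEs with complete or partial missing start/end dates will be all considered as treatment-emergent unless" one of two conditions is met. The first is "The partial start date is clearly after the 30 days of the last dose of study treatment". The second is "The partial end date is clearly before the first dose date of study treatment". The section then permits imputation of partial dates and refers the reader to Section 7.3.

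The imputation rules are in fact in SAP Section 6.3 and its Table 1. Section 6.3 also says: "If an event is ongoing, the end date will not be imputed". Protocol Section 8 has its own TEAE definition: events absent before study product, or already present and worsening in intensity or frequency.

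**The concern.** The definition turns on when the event began, whether it worsened and whether it is related. The default turns on whether a date field is complete. Where the available dates already place an event, the two can give different answers, and the SAP does not say which prevails.

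Characterising safety is a primary objective, and the AE incidence summaries in Section 11.1 are built on the TEAE flag. Two programmers could follow the same section and produce different flags for the same record.

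**Working it through.** The plan gives no figure to reproduce here, so the check applies the definition and the default to the same records.

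**Classification.** "Window" below is replaced by its meaning: first dose through last dose plus 30 days.

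| Record | Definition | Default with its exceptions |
|---|---|---|
| A. Partial start clearly pre-dose, not worsened, end date not clearly pre-dose | Not TEAE | TEAE |
| B. Complete pre-dose start, not worsened, ongoing with blank end date | Not TEAE | TEAE, if blank counts as missing |
| C. Complete start after last dose + 30 days, unrelated, ongoing with blank end date | Not TEAE | TEAE, if blank counts as missing |
| D. Partial start clearly after last dose + 30 days, unrelated | Not TEAE | Not TEAE |
| E. Partial start clearly after last dose + 30 days, related | TEAE | Excepted, so not TEAE |
| F. Complete start within the treatment window, any end date | TEAE | TEAE |

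**Case A.** The default is triggered because the start date is partial. The first exception looks only for late starts and the second only at the end date, so nothing lets an early partial start remove the event. Imputation would help. Under Table 1, a start known only to a month before the month of Study Day 1 becomes the first of that month, and a start known only to an earlier year becomes 1 January of that year. Both are pre-dose, and the definition then excludes the event. But Section 11.1 makes imputation optional, and the section it cites, 7.3, covers demographic and baseline characteristics.

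**Cases B and C.** Section 6.3 leaves an ongoing event's end date blank. Neither Section 6.3 nor Section 11.1 says whether that blank is a missing date for the default. If it is, neither exception can act, because both test partial dates only. By contrast, the concomitant-medication rule in SAP Section 11.3 tests complete as well as partial dates. In case B there is a further sign that the flag would be wrong: Protocol Section 8 closes an AE record when its grade changes and opens a new one, so a pre-dose record still open has not changed grade.

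**Case E.** The SAP's own example for the first exception is a window closing in November and a start in the following January with the day missing. If that AE is related, the third limb includes it and the exception takes it out. Such records can exist, because Protocol Section 8.5 collects related AEs after the 30 days.

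**How many records.** Protocol Section 8.5 limits pre-dose AEs to those at least possibly related to study procedures. After 30 days, AEs unrelated to product or procedures are collected only if serious or of special interest, to Day 90, or to Day 30 if new NPC therapy starts (Protocol Section 8.5.1). The documents give no AE counts. Assume 0 to 2 affected subjects.

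**Size.** SAP Section 1 gives 12 enrolled subjects; assume all were dosed.

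- One subject with no other TEAE in the row: 1/12 = 8.3 percentage points.
- Two such subjects in the same row: 2/12 = 16.7 points.
- Range under the assumption: 0 to 16.7 points. A subject who already has a TEAE in that row adds nothing.

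**The case against.** The best defence is that the default is only a fallback. It follows the definition, and both worked examples concern dates with the day missing, so a sensible programmer would use it only when the definition cannot decide. That is probably what was meant for late events with complete start dates (case C). The text does not say so, however, and it does not help case A: there the date is partial, which is exactly what triggers the default.

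The second defence is that an ongoing event has a known status, not a missing date. This is a fair reading of Section 6.3, and under it cases B and C disappear. They are therefore conditional. Case A does not depend on the point.

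The third is that the word introducing the exceptions may only lift the default and return the event to the definition. Read that way, case E disappears. The SAP does not state this either.

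A reader might infer more than the documents support:

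- That any blank end date makes an AE treatment-emergent whatever its start date. This assumes that ongoing means missing, and it fails for case D, which the first exception removes.
- That every AE table is distorted. Treatment-related tables are largely untouched by cases A to C: related events on or after first dose are TEAEs already, and a pre-dose event can hardly be attributed to a product not yet given. Case E is the one that bears on those tables.
- That the error is always an over-count. Case E is an under-count.
- That one subject moves an incidence by 1/6 = 16.7 points within a sub-cohort. This assumes a sub-cohort of six and AE tables by sub-cohort, which Section 11.1 does not specify.

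**Conclusion.** The concern holds as a conflict between a stated rule and the definition it is meant to serve. Case A is a wrong flag on the text as written unless the optional imputation is used. Cases B and C follow only if an ongoing event's blank end date is treated as missing, which the SAP leaves unsettled. Case E works in the opposite direction when the exception is read as an exclusion.

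The expected effect is small. It rests on the assumed 0 to 2 affected subjects and on all 12 having been dosed. The study stopped after Phase 1B, its safety analyses are descriptive, and Section 11.1 lists all AEs whether or not they are treatment-emergent, so a misclassified event stays visible. The point is worth settling before the TEAE flag is final because it costs almost nothing, not because it would change the safety conclusion.

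**What to change.** Apply the default only when the available dates cannot place onset. For example:

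> An AE with a missing or partial start date is treatment-emergent unless the available start or end date shows onset before first dose (and it did not worsen) or more than 30 days after last dose (and it is unrelated). A missing end date, including for an ongoing event, does not by itself make an AE treatment-emergent.

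This classifies cases A to E as the definition does and leaves F unchanged. Also correct the imputation cross-reference in Section 11.1 from Section 7.3 to Section 6.3.

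The cost is a short rewording of one paragraph, one corrected reference and one programming condition. No new data are needed.

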4.6 Subject Withdrawal Criteria

A subject may withdraw either from (1) investigational product treatment only, in which case the subject will continue protocol defined follow-up assessments or (2) study participation, in which case investigational product and study assessments will be discontinued. Whenever possible, continue protocol-defined follow-up after the subject has discontinued investigational product treatment (refer to Section [6.7](#)).

Investigational product treatment may be discontinued for any of the following reasons:

- Occurrence of an AE that precludes further treatment, refer to Section [5.2.5](#)
- Achieves a sustained CR, refer to Section [5.2.4](#)
- Receives a prohibited treatment, such as use of a different investigational product or non-protocol anti-NPC therapy
- Decision (by subject or investigator) that continued investigational product treatment is not in the subject's best interest

Study participation may be discontinued for any of the following reasons:

- Withdrawal of consent by subject or subject's legally authorized representative
- Early closure of the study by the sponsor
- Subject is lost to follow-up

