Per iRECIST (Section 7.1.4), disease progression should be confirmed by the study site 4 to 8 weeks after site-assessed first radiologic evidence of progressive disease in clinically stable subjects. Subjects, who have unconfirmed disease progression may continue on treatment at the discretion of the investigator until progression is confirmed by the site, provided they have met the conditions detailed in Section 7.1.4. Subjects who receive confirmatory imaging do not need to undergo the next scheduled tumor imaging if it is less than 4 weeks later; tumor imaging may resume at the subsequent scheduled imaging time point, if clinically stable. Subjects, who have confirmed disease progression by iRECIST, as assessed by the study site, will discontinue treatment with investigational products. Exceptions are detailed in Section 7.1.4.

7.1.2.3 *End-of-Treatment and Quarterly Follow-up Tumor Imaging*

For subjects who discontinue treatment with investigational products, tumor imaging should be performed at the End-of-Treatment Visit (30 \pm 5 days after the last dose of investigational

product). If previous imaging was obtained within 4 weeks prior to the date of discontinuation, then imaging at treatment discontinuation is not mandatory. For subjects who discontinue both investigational products due to documented disease progression, this is the final required tumor imaging if the investigator elects not to implement iRECIST.

For subjects who discontinue study treatment without documented disease progression, every effort should be made to continue monitoring disease status by tumor imaging using the same imaging schedule used while on treatment until the start of a new anticancer treatment, disease progression, pregnancy, death, withdrawal of consent, or the end of the study, whichever occurs first.

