8.1.1 Serious versus Severe Adverse Events

To avoid confusion between the terms “serious” and “severe” which have different implications in the context of a clinical study, the following definitions are provided [19]:

The term “severe” is used to describe the intensity (severity) of a specific event (as in mild/grade 1, moderate/grade 2, severe/grade 3, life-threatening/grade 4, and death/grade 5). However, the event itself may be of only minor medical significance (eg, a severe headache). This is not the same as “serious”, which is based on a subject/event outcome or action criteria

associated with events that threaten a subject's life or function. Seriousness (not severity) serves as a guide to the sponsor to determine regulatory reporting obligations.

8.1.2 *Serious Adverse Event Definition Clarifications*

Death is a result of an SAE, and not an SAE itself. The event that, in the investigator's judgment, caused the death is the SAE.

Life-threatening means that the subject was at immediate risk of death from the event as it occurred. Life-threatening does not include an event that might have led to death, had it occurred with greater severity.

In-patient hospitalization means the subjects has been formally admitted to a hospital for a medical cause, for any length of time. This may or may not be overnight. It does not include presentation and care within an emergency department (although an emergency department visit may define a medically important event, which is considered an SAE).

The principal investigator should attempt to establish a diagnosis of an event based on signs, symptoms, and test results or other medical information (when obtained). In such cases, the diagnosis should be documented as the AE rather than the individual signs or symptoms.

8.2 *Adverse Events of Special Interest*

An AE of special interest (serious or non-serious) is one of scientific and medical concern specific to the sponsor's product or program, for which ongoing monitoring and rapid communication by the investigator to the sponsor can be appropriate. Such an event might warrant further investigation in order to characterize and understand it. All AEs of special interest must be reported in a manner similar to SAEs (see Section 8.5.1).

8.2.1 *Adverse Events of Special Interest for Pembrolizumab*

AEs of special interest for pembrolizumab for this study include:

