8.5 Adverse Event Reporting Requirements

AEs, including SAEs will be reported by the subject (or, when appropriate, by the subject's legally authorized representative) to the investigator. The investigator, who is a qualified physician, and any designees are responsible for detecting, assessing, documenting, and reporting events that meet the definition of an AE in the electronic case report form (eCRF). Investigators remain responsible for following up AEs for outcome.

AE reporting requirements are as follows:

- AEs assessed by the investigator as at least possibly related to study procedure(s) occurring from the date that the first informed consent is signed to before the first dose of investigational product
- All AEs, related and unrelated, occurring from the first administration of any investigational product through 30 days after the last investigational product
- AEs assessed by the investigator as at least possibly related to any investigational product or study procedure(s) occurring after 30 days from the last investigational product exposure

In addition, for the indicated events, refer to the following sections:

- Deaths, see Section [8.5.1](#)
- SAEs, including AEs of special interest, see Section [8.5.1](#)
- Pregnancies and exposures during lactation, see Section [8.5.2](#)
- Laboratory abnormalities as an AEs, see Section [8](#)

Disease progression without secondary complications should be reported as an AE of disease progression (eg, a new metastasis or tumor increase) and not the indication for which subject entered the study (ie, EBV⁺ NPC). If the event is a complication of disease progression, the complication should be reported along with the event of disease progression (eg, a recent increase in bronchial tumor leading to pneumonia should be reported as “disease progression” and “pneumonia”).

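### All-cause TEAE rows may be inflated by disease progression by an unknown amount, and no planned summary shows them without it

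*SAP*

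**What the plan says.** Protocol 8.5 instructs sites: "Disease progression without secondary complications should be reported as an AE of disease progression". It continues: "If the event is a complication of disease progression, the complication should be reported along with the event of disease progression". Progression is therefore collected as an AE whether or not anything else happens.

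SAP 11.1 gives three alternative ways for an AE to be a TEAE. The first reads: "Any AE occurring after initiation of the first dose of study treatment through 30 days after the last administration of study treatment or". The other two cover pre-existing AEs that worsen and related AEs on or after first dose. None sets progression aside, and Protocol 9.3 adds nothing on it. The overall summary is built from this definition. It has rows for any TEAE, "TEAEs with worst grade" 3 or higher, fatal TEAEs, serious TEAEs, "TEAEs leading to any study treatment discontinuation", and interruption.

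Three protocol rules bear on how progression reaches those rows:
- Protocol 8.1.2: "Death is a result of an SAE, and not an SAE itself". The event judged to have caused the death is the SAE.
- Protocol 7.1.2.2: "Subjects, who have confirmed disease progression by iRECIST, as assessed by the study site, will discontinue treatment with investigational products". Exceptions are set out in 7.1.4.
- Protocol 4.6 lists "Occurrence of an AE that precludes further treatment" among the reasons for stopping treatment, but has no separate entry for progression.

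SAP 1 states that the study ended in Phase 1B with 12 subjects enrolled. Characterizing the safety profile is a primary objective of that phase.

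**The concern.** Progression of NPC is failure of efficacy. Once it is coded as an AE inside the treatment window, it can count in the rows most often used to describe toxicity. A death from NPC within 30 days of last dose can appear as a fatal and serious TEAE. A stop at confirmed progression can appear as a TEAE leading to discontinuation. Because that row covers any study treatment, stopping pembrolizumab alone, as Protocol 15.2.4 describes at confirmed progression, could also qualify.

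At stake is how a primary objective of the only phase that ran is read. In a single-arm study the all-cause rows have no comparator. If progression contributes to them, the combination looks more toxic than it is, and toxicity from other causes is harder to see in the total. The protocol already keeps progression out of the DLT definition (5.2.3), but the SAP does not carry that distinction into any all-cause TEAE summary.

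**Working it through.** **What the documents quantify.** They give no figure for the share of TEAEs that are progression, so there is no stated value to reproduce. The first check is of the text, row by row.

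| SAP 11.1 all-cause row | How a progression AE enters | Certain? |
|---|---|---|
| Any TEAE | Reported under Protocol 8.5 within the window | Yes, if reported |
| Grade 3 or higher | Only if graded so (Protocol 8.3) | No |
| Serious | Only if it meets a criterion in Protocol 8.1 | No |
| Fatal | Only if recorded as the event that caused death (Protocol 8.1.2) | No |
| Discontinuation | Only if the AE is recorded as leading to the stop | No; coding rule not given |

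The route exists for every row, but entry is conditional in the last four.

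**Weight of one subject.** With N = 12 (SAP 1), one subject counted only for progression adds 1/12 = 8.3 percentage points. For example, 3/12 = 25% (exact 95% CI 5.5% to 57.2%) becomes 6/12 = 50% (21.1% to 78.9%) with three such subjects.

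**Range of inflation (assumed inputs).** Let t be the proportion of subjects with a qualifying non-progression TEAE and q the proportion with a qualifying progression AE. Neither is in the documents. Assuming independence, the reported row is u = 1 − (1 − t)(1 − q), and the share of counted subjects who are there only for progression is (u − t)/u. For t = 25% and q = 50%, u = 1 − 0.75 × 0.50 = 62.5%, and the share is 37.5/62.5 = 60%.

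Each cell shows u, then the progression-only share:

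| t | q = 10% | q = 25% | q = 50% | q = 75% |
|---|---|---|---|---|
| 10% | 19.0%; 47% | 32.5%; 69% | 55.0%; 82% | 77.5%; 87% |
| 25% | 32.5%; 23% | 43.75%; 43% | 62.5%; 60% | 81.25%; 69% |
| 50% | 55.0%; 9% | 62.5%; 20% | 75.0%; 33% | 87.5%; 43% |

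The share runs from 9% to 87%. It exceeds one half in some cells and not in others. If subjects with progression also tend to have other qualifying events, for instance complications reported alongside it under Protocol 8.5, the inflation is smaller than shown.

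**Can the planned tables recover the missing rate?** Subject incidences by preferred term do not add up across terms. Suppose, hypothetically, that the serious row is 6/12 and a progression term shows 4/12. The serious rate excluding progression could be anything from (6 − 4)/12 = 16.7%, if none of the four had another serious event, to 6/12 = 50%, if all did. Other preferred-term rows may narrow this, but the summaries do not in general fix the value.

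**The case against.** The strongest reply is that the SAP already lets a reader see progression.
- SAP 11.1 repeats every headline row for events related or possibly related to each product, which should drop most progression.
- It plans preferred-term tables for all, serious, fatal and discontinuation TEAEs, and by worst grade, where progression would be visible by term.
- It summarizes the primary cause of all deaths, and SAP 7.1 summarizes reasons for treatment discontinuation.
- All AEs are listed. With 12 subjects, someone holding the listings can find those counted only for progression.
- DLTs exclude progression (Protocol 5.2.3) and have their own table.

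Most of this stands and limits the point. It does not close the gap. The related-only rows answer a different question: they rest on investigator attribution in an open-label study, and under Protocol 8.4 an event is possibly related when a link cannot be excluded. Some progression may stay in, and toxicity judged unrelated drops out. The preferred-term rows are not additive, and the examples in Protocol 8.5 (a new metastasis, tumor growth) could spread progression over several terms. Cause of death and stopping reasons do not correct the TEAE rows. Listings permit reconstruction by hand, but it is not a planned summary.

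A second objection is that removing progression could hide tumor flare, a listed tabelecleucel risk (Protocol 8.2.2, SAP 11.1) that can look like radiographic progression (Protocol 15.5). That is a sound reason to keep flare off the term list and to retain the all-cause rows.

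**Conclusion.** The all-cause grade 3 or higher, fatal, serious and discontinuation rows may be inflated by progression, by 8.3 percentage points for each subject counted only for it. The total is unknown. It depends on site grading, seriousness and discontinuation coding that the documents do not give. The tables above rest on assumed t and q and on independence. DLT incidence is not affected.

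A reader might infer that these rows will consist mostly of progression, perhaps 6 to 9 of 12 subjects (50% to 75%). The earlier series in Protocol 1.3 invites this: 14 treated less 1 CR, 2 PR and 1 SD leaves 10 (71%). The documents do not support it. That series describes tabelecleucel given before the present combination. It does not say that the 10 progressed on treatment or within 30 days, and it gives no rate of serious, severe, fatal or discontinuation-coded progression events. Nor do the documents support the inference that progression cannot be separated at all, given the preferred-term tables and listings.

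What remains is a specific, inexpensive gap in the summary of a primary safety objective: no planned summary gives all-cause rates excluding progression.

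**What to change.** In SAP 11.1, before database lock:
1. Prespecify the MedDRA preferred terms that represent progression of NPC. Do not include tumor flare.
2. Show the headline rows side by side, with all TEAEs and with those terms excluded. Keep the all-cause rows, and do not name the excluded rows as the main description of safety.
3. State whether stopping a study treatment for progression is counted as a TEAE leading to discontinuation, consistently with the reasons summarized under SAP 7.1.
4. Add a footnote that complications of progression reported as separate AEs remain in both sets of rows.

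The cost is one repeated summary table, a short term list and a few sentences of SAP text. No new data are needed.
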